10.2 Evaluations During Treatment

10.2.1 The following laboratory assessments will be performed weekly during the first cycle and second cycle

- Hematology: CBC with differential
- Serum chemistries: Na, K, Cl, HCO₃, glucose, blood urea nitrogen (BUN), creatinine, calcium, magnesium, phosphate, total bilirubin, AST, ALT, alkaline phosphatase, albumin, and total protein.
- Peripheral blood sample for flow cytometry for B:T cell ration will be drawn on cycle 1 day 8
- Serum pregnancy test –All females of childbearing potential should complete a serum pregnancy test within 7 days prior to the administration of blinatumomab on day 1 of cycle 1. The test will be repeated on day 1 of cycle 2.

10.2.2 The following clinical assessments are to be performed on weekly every cycle (± 3 days). Procedures and examinations may be performed more frequently if clinically indicated:

- Brief physical examination
- Vital signs, including weight, temperature, pulse, blood pressure, respiratory rate, and oxygen saturation
- ECOG Performance Status;
- Recording of AEs (patients and/or family members will be instructed to telephone the site with any changes in mental or physical status or with any questions regarding treatment)
- Recording of concomitant medications.

10.2.3 The following objective disease assessments are to be performed within the 7 days prior to beginning cycle 2.

- Full body CT and PET scans (or preferably a single combined-modality PET-CT scan). Neck imaging is only required if baseline neck imaging showed lymphoma involvement.
- Bi-dimensional measurement of up to 3 of the largest target lesions.
- Measurements will be made by the DF/HCC tumor imaging metric core (TIMC).

10.3 Post Treatment Evaluations

- Subjects without progression will be seen every 3 months for the first 2 years with CT scans every 6 months. After 2 years, subjects will be seen every 6 months with CT scans annually through 5 years.

- Hematology: CBC with differential
- Serum chemistries: Na, K, Cl, HCO₃, glucose, blood urea nitrogen (BUN), creatinine, calcium, magnesium, phosphate, total bilirubin, AST, ALT, alkaline phosphatase, albumin, and total protein.
- Brief physical examination
- Vital signs, including weight, temperature pulse, blood pressure, respiratory rate, and oxygen saturation
- ECOG Performance Status;
- Recording of AEs (patients and/or family members will be instructed to telephone the site with any changes in mental or physical status or with any questions regarding treatment)
- Recording of concomitant medications.
- Contrast enhanced CT scan of the chest, abdomen, and pelvis with tumor measurements will be performed every 6 months (+/- 7 days) beginning 6 months following the end of treatment restaging scan for two years and then annually through 5 years or until disease progression

10.4 End of study evaluations

When a patient is removed from study, end of study assessments are to be performed within 30 days (+/- 2 days). If the patient is not available, the reason for not completing the end of study assessments must be recorded in the patient's source documents.

The following clinical assessments will be performed:

- Full physical examination
- Weight and vital signs (blood pressure, pulse rate, respiratory rate, oxygen saturation, and temperature)
- ECOG Performance Status
- Recording of AEs
- Recording of concomitant medications

The following laboratory assessments will be performed:

- CBC with differential and platelet count
- Serum chemistries: Na, K, Cl, HCO₃, glucose, blood urea nitrogen (BUN), creatinine, calcium, magnesium, phosphate, total bilirubin, AST, ALT, alkaline phosphatase, albumin, and total protein

Patients will be followed for 1 year after the last cycle of therapy for toxicity and duration of response (if applicable). The following procedures will be completed:

- Recording of AEs (patients and/or family members will be instructed to telephone the site with any changes in mental or physical status) for 90 days following their last dose of blinatumomab.

Visit evaluation schedule

1. Baseline evaluations must be performed \leq 45 days prior to cycle 1 administration of blinatumomab, unless otherwise stated.
2. Physical examination, vital signs, weight, height – Physical examinations, vital signs, and weight will be performed on the scheduled day, even if study medication is being held. More frequent examinations may be performed at the investigator's discretion, if medically indicated. If these baseline examinations were performed \leq 72 hours prior to the first dose of blinatumomab, they need not be repeated on day 1 of cycle 1. Vital signs (weight, temperature, respiratory rate, oxygen saturation, sitting blood pressure, and sitting pulse) should be performed weekly unless otherwise indicated. .
3. ECOG performance status –Assessment of ECOG Performance Status will be performed on the scheduled day, even if study medication is being held. More frequent examinations may be performed at the investigator's discretion, if medically indicated. If the baseline assessment was performed \leq 72 hours prior to the first dose of blinatumomab, then it does not need to be repeated on day 1 of cycle 1.
4. PET/CT Scan will be performed at baseline, 6 weeks after completion of the first cycle, and 6 weeks after completion of the second cycle. Staging will then be performed with CT scans of the chest, abdomen, and pelvis every 6 months for the first 2 years and then annually for 5 years or until progression. Neck CT after baseline study is only required if neck was involved on baseline imaging.
5. Hematology –Hematology should be performed at baseline, weekly during cycle 1 and 2, every 3 months during follow up, and at the time of study treatment completion
6. Coagulation –The coagulation profile must be performed at baseline only and repeated only as clinically indicated
7. Biochemistry –Biochemistry should be performed at baseline, weekly during cycle 1 and 2, every 3 months during follow up, and at the time of study treatment completion. Subjects will have hepatitis serologies, LDH, and beta-2 microglobulin drawn at baseline.
8. Peripheral blood flow cytometry for calculation of absolute b and t lymphocytes should be performed at baseline and on day 8 of cycle 1.
9. Serum pregnancy test –All females of childbearing potential should complete a serum pregnancy test within 7 days prior to the administration of blinatumomab on day 1 of cycle 1. The test will be repeated on day 1 of cycle 2.
10. Prior/concomitant medications –Record all medications administered \leq 30 days prior to the administration of blinatumomab. Record all medications taken during the study on the Concomitant Medications eCRF.
11. Adverse events –. Subjects must be instructed to notify the investigator concerning any undesirable symptoms or side-effects while on study. Adverse event monitoring should be continued for at least 4 weeks following the last dose of study treatment. Antineoplastic therapies since discontinuation of study drug – All cancer medications/therapies given to a subject after the last dose of study drug must be recorded in the Antineoplastic therapies since discontinuation of study drug eCRF. This should be done monthly for the first 6 months, then once every 3 monthly thereafter until disease progression or subject receives new antineoplastic therapies whichever happens first.

12. Subjects without progression will be seen every 3 months for the first 2 years with CT scans every 6 months. After 2 years, subjects will be seen every 6 months with CT scans annually through 5 years.

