1. OBJECTIVES

1.1 Study Design

This will be an open label single arm phase II study employing a Simon's optimal two stage design to assess efficacy and safety of blinatumomab in indolent NHL. Blinatumomab will be administered as a continuous IV infusion with stepwise dosing reaching a target dose of at 112mcg/d for 28 days. Subjects will start at a dose of 9 mcg/d with escalation to 28mcg/d and 112mcg/d if no toxicity at 7 day intervals. Subjects will be restaged 6 weeks after completion of the infusion by PET CT. All subjects without disease progression will receive an additional 4 week cycle. All subjects will then have an end of treatment PET CT 6 weeks after completion of the second infusion. All subjects with a response will then be followed with a CT every 6 months for 2 years then annually through 5 years or until progression.

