7.3 Expedited Adverse Event Reporting

7.3.1 Investigators **must** report to the Overall PI any serious adverse event (SAE) that occurs after the initial dose of study treatment, during treatment, or within 30 days of the last dose of treatment on the local institutional SAE form.

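### Section 10.4 ends duration-of-response follow-up at 1 year, against 5 years everywhere else it is stated, and the adverse-event recording period after the last dose is inconsistent

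*Combined protocol and SAP*

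**What the plan says.** **Response follow-up.** Section 1.1 states: "All subjects with a response will then be followed with a CT every 6 months for 2 years then annually through 5 years or until" (the sentence closes by naming disease progression as the other end point). Section 10.3 covers subjects without progression: "After 2 years, subjects will be seen every 6 months with CT scans annually through 5 years". Section 5.1, items 4 and 12 of the visit evaluation schedule, section 11.1 and section 13.2 agree on 5 years. Section 11.6 measures duration of response up to objectively documented recurrence or progression and sets no time limit. Section 10.4 alone differs: "Patients will be followed for 1 year after the last cycle of therapy for toxicity and duration of response (if applicable").

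**Adverse events after the last dose.**
- Section 10.4, directly beneath the 1-year sentence, has AEs recorded "for 90 days following their last dose of blinatumomab".
- Visit schedule item 11: "Adverse event monitoring should be continued for at least 4 weeks following the last dose of study treatment".
- Section 10.3 lists AE recording among its post-treatment evaluations without an end date: "Recording of AEs (patients and/or family members will be instructed to telephone the site with any changes in mental or physical status or with" (the remainder concerns queries about treatment). Those visits run to 5 years and are for subjects without progression.
- Section 7.3.1 requires SAEs to be reported to the Overall PI if they occur during treatment or "within 30 days of the last dose of treatment on the local institutional SAE form".
- Section 7.6 requires all AEs to reach the Overall PI through routine data submission.
- Section 5.5 follows subjects taken off therapy for an unacceptable AE monthly until that event resolves or stabilises.

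No section says which period governs. Duration of response, PFS and adverse events are secondary endpoints in section 13.1.

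**The concern.** Duration of response is informative only if responders are watched long enough to relapse. The protocol's own rationale (section 2.3) quotes a median of 26 months in indolent NHL, so a 12-month limit would stop observation well before half of such responses had ended. A site that reads 10.4 literally could close response follow-up at 1 year while another continues to year 5. The censoring pattern would then reflect which section was followed.

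On safety, a subject's count of late adverse events could depend on the section applied and on outcome. A non-progressor has AE recording listed at visits through year 5, while a subject who has progressed has only item 11 and 10.4. Pooled AE rates would then mix different observation periods.

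**Working it through.** **1. The plan's own duration figure.** Section 13.2 gives enrolment within 3 years, 5 years of follow-up and an 8-year study. 3 + 5 = 8 reproduces it. Under the 1-year sentence, follow-up would end at about 3 + 1 = 4 years. The statistical section therefore assumes 5 years.

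**2. Scans lost under a 1-year limit.** The end-of-treatment scan is 6 weeks after the last infusion, or 6/4.345 = 1.4 months. Section 10.3 starts the follow-up CTs 6 months after that scan, so they fall at 6, 12, 18, 24, 36, 48 and 60 months after it. Adding 1.4 gives 7.4, 13.4, 19.4, 25.4, 37.4, 49.4 and 61.4 months after the last infusion. Taking the year from the end of that infusion, 1 of the 7 CTs falls within 12 months.

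**3. Relapses inside each period.** Assume exponential response duration, and treat 12 and 60 months as time since response. The proportion relapsed by time t is 1 - 0.5^(t/median).

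| Median (months) | By 12 months | By 60 months |
|---|---|---|
| 26 (section 2.3) | 1 - 0.5^(12/26) = 0.27 | 1 - 0.5^(60/26) = 0.80 |
| 15.4 | 0.42 | 0.93 |
| 36 | 0.21 | 0.69 |

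The 15.4 is reported in section 2.2.7 as a mean, for all NHL types at the 60 µg/m²/day level; it is used here as an assumed low median. The 36 is an assumption with no source in the documents. At the 26-month median, 1 - 0.27 = 73% of responders would be censored at 1 year, and a median near 26 months could not be estimated.

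**4. The AE periods side by side.**
- 10.4: 1 year for toxicity, with a 90-day recording procedure beneath it.
- Item 11: at least 28 days, a minimum.
- 10.3: no end date, at visits through 5 years, non-progressors only.
- 7.3.1: 30 days, for SAE reports to the Overall PI. This is a reporting duty for serious events, not a collection window for all AEs. It ends 90 - 30 = 60 days before the 90-day recording does.

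**5. Primary design.** For the two-stage rule (at least 6 of 13, then at least 15 of 28), the probability of success is the sum over x = 6 to 13 of P(X1 = x) × P(X2 ≥ 15 - x), with X1 ~ Bin(13, p) and X2 ~ Bin(15, p). This gives 0.0930 at p = 0.40 and 0.9035 at p = 0.65, with early-stop probabilities of 0.574 and 0.046. The plan states 0.093, 0.904, 0.57 and 0.05. None of these depends on follow-up length.

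**The case against.** The best defence on response is that the 5-year intent is plain: the 1-year sentence stands alone, and the 5-year schedule covers all responders or non-progressors, including those who stopped therapy early. That stands as evidence of intent, but the sentence remains current text on a secondary endpoint and no rule of precedence overrides it. Nor does it help to read 10.4 as covering only off-study subjects. Section 5.6 limits off-study to loss to follow-up, withdrawn consent for data submission and death, after which a year of toxicity and response follow-up is not workable.

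Several stronger readings are tempting, and the documents do not support them:
- **Four contradictory AE end dates.** The 30 days in 7.3.1 is an SAE reporting window, and a reporting window may be shorter than a collection window. Item 11 sets a floor, so a site recording for 90 days satisfies both it and the 10.4 procedure. The remaining ambiguity is 90 days against 1 year within 10.4, and against the open-ended recording in 10.3.
- **SAEs on days 31 to 90 never reach the sponsor.** Section 7.6 still sends every AE to the Overall PI routinely, and 7.4 puts no 30-day limit on FDA reporting. What ends at 30 days is the specific SAE reporting duty in 7.3.1.
- **The 1-year sentence applies only to subjects who came off therapy.** Section 5.5 and Table 6-1 do use removal from study for treatment stoppers, but the sentence refers to patients without restriction.
- **About 10 of 28 subjects would be censored early.** Table 2-2 shows 34/95 (35.8%) of NHL patients stopping for an AE, and 28 × 34/95 = 10.0. Those are all stoppers, not responders, and sections 11.2 and 13.3.2 make subjects who stop in cycle 1 without progression non-evaluable for response.

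It is also fair that the effect on AE rates is unquantified. Sections 2.2.6 and 2.4.1 place the greatest risk in the first days of treatment, so late differences may be small.

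**Conclusion.** The contradiction on duration of response is real: 1 year in one sentence of 10.4, against 5 years in sections 1.1, 5.1, 10.3, 11.1 and 13.2 and visit schedule items 4 and 12. Following the 1-year sentence would cut the share of relapses falling inside follow-up from about 80% to about 27% at a 26-month median (69-93% to 21-42% over the assumed range). These figures rest on an exponential model, and the 26-month median comes from a group in which only 8 of 9 subjects responded. They show what the sentence would do if obeyed; they do not predict how many sites or subjects would follow it.

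The AE point holds in narrower form: the recording period is not settled within 10.4 or between 10.4 and 10.3, item 11 gives only a minimum, and the 10.3 recording depends on being progression-free. The shorter SAE reporting window is a misalignment to explain, not a contradiction. The consequences are confined to secondary efficacy and safety endpoints.

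**What to change.** 1. In 10.4, delete duration of response from the 1-year sentence, so that every responder without progression, on or off therapy, follows the 5-year schedule in 10.3.
2. State one AE collection window after the last dose, applied to all subjects whether or not they have progressed, and use it in 10.3, 10.4 and visit schedule item 11. This must also settle the 1-year toxicity phrase in 10.4 and say what AE recording at the 10.3 visits covers. Changing only 7.3.1 and item 11 would leave the conflict in place.
3. Align the SAE window in 7.3.1 with that period, or state why it is shorter.

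The cost is an amendment of wording, possibly a few more SAE reports, and some AE contacts for subjects who have progressed. Subjects already on the 3-monthly schedule need no added visits, and the sample size and decision rule do not change.

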11. MEASUREMENT OF EFFECT

11.1 Antitumor Effects

Response and progression will be evaluated in this study using the modified Cheson criteria for lymphoma response.(14)

- Patients will be assessed for response at 6 weeks after the conclusion of cycle 1 (within 7 days of day 84) using a CT scan of the chest, abdomen and pelvis, as well as a full body PET scan (preferably a combined modality PET-CT scan will be used). Neck CT only required if involved on baseline imaging.
- Patients who continue on study (non-progressors) will be re-evaluated at 6 weeks after the conclusion of cycle 2 (within 7 days of day 168) using a CT scan of the chest, abdomen and pelvis, as well as a full body PET scan (preferably a combined modality PET-CT scan will be used). Neck CT only required if involved on baseline imaging.
- Patients who continue on study (non-progressors) after 2 cycles will be assessed using a CT scan of the chest, abdomen and pelvis every 6 months for 2 years and then annually for 5 years or until progression. Neck CT only required if involved on baseline imaging.

11.2 Definitions

Evaluable for toxicity. All patients who receive at least one dose of study drug will be evaluable for toxicity.

Evaluable for objective response. Only those patients who have received at least one complete cycle of therapy, and have had their disease re-evaluated will be considered evaluable for response. Subjects removed from study for disease progression prior to a full cycle of therapy will also be considered evaluable for response. These patients will have their response classified according to the definitions stated below.

11.3 Disease Parameters

Measurable disease. Measurable lesions are defined as those that can be accurately measured in at least one dimension (longest diameter to be recorded) as ≥ 20 mm with conventional techniques (CT, MRI, x-ray) or as ≥ 10 mm with spiral CT scan. All tumor measurements must be recorded in millimeters (or decimal fractions of centimeters).

Non-measurable disease. All other lesions (or sites of disease), including small lesions (longest diameter <20 mm with conventional techniques or <10 mm using spiral CT scan), are considered non-measurable disease. Bone lesions, leptomeningeal disease, ascites, pleural/pericardial effusions, lymphangitis cutis/pulmonis, inflammatory breast disease, abdominal masses (not followed by CT or MRI), and cystic lesions are all non-measurable.

11.4 Methods for Evaluation of Measurable Disease

All measurements should be taken and recorded in metric notation using a ruler or calipers. All baseline evaluations should be performed as closely as possible to the beginning of treatment and never more than 4 weeks before the beginning of the treatment.

The same method of assessment and the same technique should be used to characterize each identified and reported lesion at baseline and during follow-up. Imaging-based evaluation is preferred to evaluation by clinical examination when both methods have been used to assess the antitumor effect of a treatment.

Clinical lesions Clinical lesions will only be considered measurable when they are superficial (e.g., skin nodules and palpable lymph nodes). In the case of skin lesions, documentation by color photography, including a ruler to estimate the size of the lesion, is recommended.

CT and MRI These techniques should be performed with cuts of 10 mm or less in slice thickness contiguously. Spiral CT should be performed using a 5 mm contiguous reconstruction algorithm. This applies to tumors of the chest, abdomen, and pelvis. Head and neck tumors and those of extremities usually require specific protocols.

11.5 Response Criteria

11.5.1 Complete Response (CR)

CR requires **all** of the following:

1. **PET positive prior to therapy:** mass of any size permitted if PET negative with a score of 3 or less on the Deauville five point scale.

1-no uptake or no residual uptake

2-slight uptake, but below mediastinal blood pool

3-uptake above mediastinal, but below or equal to uptake in the liver

4-uptake slightly to moderately higher than liver

5-markedly increased uptake or any new lesion

New sites of FDG-avidity felt unrelated to lymphoma (Deauville 3 or less) will be considered CR but imaging should be repeated 6-8 weeks later to insure resolution of inflammatory changes.

2. Variably FDG-avid or PET negative prior to therapy: regression to normal size on CT (≤ 1.5 cm in their greatest transverse diameter for nodes ≥ 1.5 cm before therapy). Previously involved nodes that were 1.1 to 1.5 cm in their greatest transverse diameter before treatment must have decreased to <1 cm in their greatest transverse diameter after treatment, or by more than 75% in the sum of the products of the greatest diameters (SPD).
3. The spleen, if considered to be enlarged before therapy on the basis of a CT scan, must have regressed in size and must not be palpable on physical examination.

11.5.2 Partial Response (PR)

1. $\geq 50\%$ decrease in SPD of up to 6 largest dominant masses
 - a. FDG-avid or PET positive prior to therapy: one or more PET positive at previously involved site with a Deauville score >3
 - b. Variably FDG-avid or PET negative: regression on CT
2. No new sites of disease or increase in the size of the other nodes, liver, or spleen.
3. Splenic and hepatic nodules must regress by at least 50% in the SPD.

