11.5.3 Stable Disease (SD)

Stable disease is defined as less than a PR (see above) but is not progressive or relapsed disease FDG-avid or PET positive prior to therapy: PET positive at prior sites of disease and no new sites on CT or PET. Variably FDG-avid or PET negative: no change in size of previous lesions on CT

11.5.4 Progressive Disease (PD) or Relapsed Disease (RD):

1. Appearance of a new PET positive (Deauville 4 or 5) lesion(s) > 1.5 cm in any axis, $\geq 50\%$ increase in SPD of more than one node, or $\geq 50\%$ increase in longest diameter of a previously identified node > 1 cm in short axis..
2. $>50\%$ increase from nadir in the SPD of any previous lesions

New sites of FDG-avidity felt unrelated to lymphoma (Deauville 3 or less) not be considered PD or ED, but imaging should be repeated 6-8 weeks later to insure resolution of inflammatory changes.

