13. STATISTICAL CONSIDERATIONS

13.1 Study Design/Endpoints

Primary

- Overall Response Rate by the revised response criteria for malignant lymphoma (2014)

Secondary

- Clinical: Duration of response, time to response, progression-free survival, and overall survival
- Safety: Discontinuation of drug due to toxicity, adverse events

Exploratory

- Association of response and CNS toxicity with B:T lymphocytes ratio in peripheral blood
- Association of MRD status with progression free and overall survival

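### As written, section 11.5.2 item 1a leaves a PET-negative subject who misses CR only on a palpable spleen without a clear route to PR, so a major response may not count in the ORR

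*Combined protocol and SAP*

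**What the plan says.** The primary endpoint is the overall response rate (section 13.1). It is judged at 6 or more responses in 13 subjects and then 15 or more in 28 (section 13.2). Section 13.1 names the 2014 criteria, but section 11.2 makes the protocol's own text the working rule: "These patients will have their response classified according to the definitions stated below".

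For a subject who was PET positive before treatment, that text says:

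- **CR, section 11.5.1.** Every listed item must be met. Item 1 is met on PET alone: "mass of any size permitted if PET negative with a score of 3 or less on the Deauville five point scale". Item 3 adds that a spleen enlarged at baseline "must have regressed in size and must not be palpable on physical examination".
- **PR, section 11.5.2.** Item 1 asks for at least a 50% "decrease in SPD of up to 6 largest dominant masses". Beneath it, item 1a covers baseline-PET-positive disease: "FDG-avid or PET positive prior to therapy: one or more PET positive at previously involved site with a Deauville score >3". Item 2 asks for "No new sites of disease or increase in the size of the other nodes, liver, or spleen". Item 3 asks that splenic and hepatic nodules shrink by at least half.
- **SD, section 11.5.3.** A lead sentence defines SD as anything short of PR that is not progression or relapse. A PET description follows: "PET positive at prior sites of disease and no new sites on CT or PET".
- **PD, section 11.5.4.** This needs a new PET-positive lesion or growth of existing disease.

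**The concern.** CR and PR should meet without a gap: a subject with a large tumour reduction who just misses CR should be PR. For baseline-PET-positive disease they do not clearly meet. CR can fail on a finding unrelated to PET (the spleen), while PR as worded presupposes that PET is still positive. A subject can therefore be too good on PET for PR and not good enough on palpation for CR.

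This makes the rule non-monotone: clearing the last PET-positive site can move a subject from PR to non-responder. ORR drives both Simon decisions, so at a boundary one such subject could decide whether the trial continues or whether the regimen is called worthy of further study. The wording also allows two readings, which puts the primary endpoint at the mercy of the reader.

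**Working it through.** **Step 1. Apply the rules to one subject.** At baseline the subject is PET positive with an enlarged spleen. After treatment all sites are Deauville 3 or less, SPD is down by 50% or more, there are no new lesions, and the spleen is smaller but still palpable.

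| Category | Rule that decides | Result |
|---|---|---|
| CR | 11.5.1 item 1 met; item 3 not met (spleen palpable) | No |
| PR | 11.5.2 items 1, 2 and 3 met; item 1a describes a site above Deauville 3, and there is none | No, if 1a is a condition; yes, if 1a is descriptive |
| PD | 11.5.4: no new lesion, no growth | No |
| SD | 11.5.3 lead sentence met; PET description not met | Yes by the lead sentence; otherwise unclassifiable |

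On the strict reading of 1a the subject is not a responder, whichever way SD is read. Change one fact, a single prior site at Deauville 4, and item 1a is met: the subject is PR.

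For baseline-PET-positive disease the spleen item is the only listed way to miss CR once all sites are Deauville 3 or less, because item 1 accepts a mass of any size and item 2 is for disease that was variably avid or PET negative. That locates the gap and also shows that it is narrow.

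**Step 2. Reproduce the design.** Inputs from section 13.2: n1 = 13, continue if X1 ≥ 6, 15 more subjects, success if the total is ≥ 15 of 28, null 0.40, alternative 0.65.

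- P(success | p) = Σ over x = 6 to 13 of Bin(x; 13, p) × P(Bin(15, p) ≥ 15 − x)
- P(early stop | p) = P(Bin(13, p) ≤ 5)

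| Quantity | Stated | Computed |
|---|---|---|
| Alpha (p = 0.40) | 0.093 | 0.0930 |
| Power (p = 0.65) | 0.904 | 0.9035 |
| Early stop (p = 0.40) | 0.57 | 0.574 |
| Early stop (p = 0.65) | 0.05 | 0.046 |

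The design figures are correct.

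**Step 3. Illustrate the effect.** Let m be the share of true responders scored as non-responders through this gap. The recorded rate is p(1 − m). **The values of m are assumptions; the documents contain nothing from which to estimate it.**

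| m | Recorded ORR when true ORR is 65% | Power | Early stop | Success probability when true ORR is 40% |
|---|---|---|---|---|
| 0 | 0.65 | 0.904 | 0.046 | 0.093 |
| 1% | 0.65 × 0.99 = 0.6435 | 0.891 | 0.051 | 0.086 |
| 2% | 0.65 × 0.98 = 0.637 | 0.878 | 0.057 | 0.079 |
| 5% | 0.65 × 0.95 = 0.6175 | 0.831 | 0.077 | 0.062 |
| 10% | 0.65 × 0.90 = 0.585 | 0.732 | 0.119 | 0.039 |

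Both success probabilities fall as m rises: power is lost and alpha is not inflated.

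**Step 4. How often one subject could matter.** At a true ORR of 65%, the chance of exactly 6 of 13 is 0.083, and the chance of passing stage 1 and finishing on exactly 15 of 28 is 0.060. Only in those cases would losing one responder reverse that decision.

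**The case against.** **Item 1a may only be descriptive.** CR states that all its items are needed; PR carries no such statement. Items 1a and 1b sit under the SPD criterion and can be taken to describe the usual PET picture of a partial response, in which case the subject is PR. This stands as a possible reading. It does not remove the problem, because the text does not choose between the readings and no other section assigns this subject to PR.

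**A reader might infer that the subject fits no category at all.** The documents do not support that. The lead sentence of section 11.5.3 makes SD a residual class, and this subject falls into it. Only if the PET description is taken as a further requirement is there no category. The effect on ORR is the same either way.

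**The case is narrow.** It needs PET positivity and splenomegaly at baseline, PET clearance, and a spleen that has shrunk but is still palpable. Section 3.1.1 requires prior splenectomy in splenic marginal zone lymphoma, which removes an obvious source; follicular and other marginal zone lymphoma remain eligible without that requirement. Response is also assessed after each of two cycles, so if ORR is scored as best response, which the protocol does not state, a subject who met PR or CR at either scan is not lost. All of this stands and limits the size.

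**Imaging is preferred to examination.** Section 11.4 says so where both have been used. CR item 3 nevertheless asks for palpation expressly, so the general preference does not clearly override it.

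**A reader might infer that item 2 is a second defect**, because it bars any growth of other nodes, liver or spleen without a threshold, while nodal progression needs 50%. That does not follow. A stricter bar for PR than for PD is not a contradiction, since SD lies between them. Tying item 2 to section 11.5.4 would let a node grow by almost 50% in a subject still counted as PR, which loosens the primary endpoint.

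**Conclusion.** The point holds in a limited form. As written, a baseline-PET-positive subject who becomes PET negative with at least a 50% SPD fall, and misses CR only on a palpable spleen, is SD or unclassifiable and is not counted as a responder; a worse PET result would have made the same subject PR. Because item 1a can also be read descriptively, the scoring of such a subject depends on the reader.

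The size is unknown. The case should be uncommon, and the documents give no rate of splenomegaly or of this combination. The power figures of 0.878 and 0.831, for 2% and 5% of true responders lost, show sensitivity and are not estimates. The direction is clear: ORR and power fall, alpha is not inflated, and the stated 0.093 and 0.904 remain right for the ORR they assume. A reader might infer that the trial is underpowered as planned; the documents do not support that, since the loss depends wholly on an unquantified frequency and on the strict reading of item 1a.

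The conclusion rests on the protocol's own definitions governing classification, as section 11.2 says. The 2014 criteria were not available for comparison.

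**What to change.** Before any response is scored, reword section 11.5.2 item 1a to this effect: a subject who was FDG-avid or PET positive before therapy, has at least a 50% decrease in SPD, does not meet CR, and meets items 2 and 3, is PR whatever the residual Deauville score, including Deauville 3 or less when CR fails only on the spleen criterion.

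Leave item 2 as it stands.

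The cost is one wording change in the response definitions. It needs no extra scan, reader or subject, and the sample size, decision rules and stated error rates do not change. If scoring has already begun, make the change without reference to the results and note any subject whose category it alters.
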